4.3 Screen Failure

Screen failures are defined as patients who provide signed written informed consent to participate in the clinical trial but are not subsequently enrolled as they do not meet all required criteria. A minimal set of screen failure information is required to ensure transparent reporting of screen failure patients to meet the Consolidated Standards of Reporting Trials (CONSORT) publishing requirements and to respond to queries from regulatory authorities. Minimal information is defined as demography, screen failure reasons, eligibility criteria, and any SAEs, including AESIs.

Patients can be rescreened once before randomization in case of non-evaluable exclusion criteria or in cases where original screen failure was due to reasons expected to change at rescreening and based upon the investigator's clinical judgment. Patients can be rescreened for any other reasons or situations, if deemed necessary, at the investigator's discretion. Rescreened patients will repeat the screening visit procedures/assessments, including signing of a new informed consent form (ICF) and allocation of a new patient number.

4.4 Discontinuation From Study Drug and/or Withdrawal From the Trial

4.4.1 Discontinuation From Study Drug Treatment

All efforts should be made to keep patients on the study drug treatment. If the study drug is stopped, it should be determined whether the discontinuation can be made temporarily; permanent study drug discontinuation should be the last resort. Any study drug discontinuation should be fully documented in the electronic case report form (eCRF).

4.4.1.1 Permanent Discontinuation

In rare instances, it may be necessary for a patient to permanently discontinue the study drug.

Patients will be followed up according to the trial procedures specified in this protocol up to the scheduled date of trial completion, or up to recovery or stabilization of any AE, whichever comes last.

If possible, and after the permanent discontinuation of study drug treatment, patients will be assessed using the procedure normally planned for the last dosing day with the study drug. See the SoE ([Section 13.2](#)) for data to be collected at the time of study drug discontinuation and follow-up and for any further evaluations that need to be completed.

All cases of permanent study drug discontinuation must be recorded by the investigator in the appropriate pages of the eCRF when confirmed.

4.4.1.2 Temporary Discontinuation

Temporary study drug discontinuation decided by the investigator corresponds to more than 1 dose not administered to the patient.

Temporary study drug discontinuation may be considered by the investigator because of suspected AEs or for other reasons (eg, other medical issues). If study drug treatment is interrupted due to an AE, treatment will be reinitiated under close and appropriate clinical/and or laboratory monitoring if the investigator deems the relationship of the event to study drug as unlikely and if the trial inclusion criteria are still met.

The duration of temporary study drug discontinuation should be recorded in the appropriate eDiary pages when confirmed.

4.4.2 Lost to Follow-Up

Patients will be considered lost to follow-up if they repeatedly fail to return for scheduled visits and are unable to be contacted by the site.

The following actions must be taken if a patient fails to return to the clinic for a required trial visit:

- The site must attempt to contact the patient and reschedule the missed visit as soon as possible. The patient should be counselled on the importance of maintaining the assigned visit schedule and asked whether they wish to and/or should continue in the trial.
- Before a patient is deemed lost to follow-up, the investigator or designee must make every effort to regain contact with the patient. The methods to contact the patient include 2 phone calls or local equivalent methods (eg, sending an email to patient's last known email address). These contact attempts should be documented in the patient's source documents.

If the patient continues to be unreachable, they will be considered to have withdrawn from the trial.

4.4.3 Handling of Withdrawals

Patients are free to withdraw from the trial at any time upon request. Their participation in the trial may be stopped at any time at the discretion of the investigator or at the request of the sponsor.

If the patient withdraws consent for disclosure of future information, the sponsor may retain and continue to use any data collected before such a withdrawal of consent.

If a patient withdraws from the trial, they may request destruction of any samples taken and not tested, and the investigator must document this in the site trial records.

Patients who permanently discontinue the study drug or active participation in the trial will no longer receive the study drug. When a patient withdraws from the trial, the reason(s) for withdrawal shall be recorded by the investigator on the relevant page of the eCRF.

A patient may withdraw from the trial or study drug treatment for circumstances that include, but are not limited to, the following:

- The patient intends to become pregnant.
- The patient may be withdrawn at the discretion of the investigator due to noncompliance or due to a safety concern.

- The patient will be withdrawn if they are starting any drugs that interfere with glucose metabolism (eg, systemic glucocorticoid therapy).
- If the fasting or the mean SMPG value is >300 mg/dL, the investigator will schedule an unplanned visit as soon as possible, to obtain confirmatory FPG and investigate the cause. If no apparent or intercurrent cause is detected, the patient may be withdrawn.
- The patient has recurrent severe hypoglycemia or recurrent nocturnal hypoglycemia during the treatment period that poses a potential risk to the patient, as judged by the investigator.
- The patient needs dialysis, as judged by the investigator.
- The patient is unable to comply with the trial protocol, at the investigator's discretion.

All patients who discontinue study drug treatment will be followed up per the methods specified in this protocol. All patients who withdraw from the trial prematurely will, as soon as possible, undergo all end-of-trial and follow-up assessments/procedures at a visit that should be identified as "the early trial discontinuation visit." Patients who fail to return for final assessments will be contacted by the site in an attempt to have them comply with the protocol requirements.

Patients who withdraw from study drug treatment should be explicitly asked about the contribution of possible AEs to their decision, and any AE information elicited must be documented on the relevant page of the eCRF and in the source documents.

It is vital to obtain follow-up data on any patients who withdrew because of an AE or SAE. In every case, all efforts must be made to return the patient to the site as soon as possible to perform protocol-specified, safety follow-up procedures ([Section 13.2](#)).

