5.11 Prior and Concomitant Therapy

[figure not shown]
A concomitant medication is any treatment received by the patient concomitantly to the study drug. Recording of prior and concomitant medications will be done at the time points specified in the SoE ([Section 13.2](#)).

Use of all concomitant medications will be recorded in the patient's eCRF. The minimum requirement is that the drug name and the dates of administration are be recorded; this includes all prescription drugs, herbal products, vitamins, minerals, and OTC medications. Any changes in concomitant medications will also be recorded in the patient's eCRF.

Dose changes and any treatments in addition to the study drug should be kept to a minimum during the study. However, if these are considered necessary for the patient's welfare and are unlikely to interfere with the study drug, they may be given at the discretion of the investigator, with a stable dose (when possible). It is the responsibility of the investigator to ensure that details regarding the concomitant medication are recorded in full in the eCRF. The Gla-300 and IDeg-100 labels should be consulted for any additional information regarding concomitant medication administration.

The following medication(s) are not permitted during the screening and randomized, open-label treatment periods of the trial:

- Any type of glucose-lowering agents other than the study drug, protocol-allowed background noninsulin antidiabetic drug(s) ([Section 5.2.1](#)), and when applicable, rescue therapy ([Section 5.2.2](#)) are to be used. (Note: Short-term [≤ 10 days] use of short- or rapid-acting insulin therapy [eg, due to acute illness or surgery] is allowed.)
- Potential novel therapies like dual GIP and GLP-1 RA.
- Noninsulin antidiabetic drugs, which are not approved for combination with insulin according to local labeling/local treatment guidelines.
- Insulin pump therapy.
- Weight loss drugs (including OTC and herbal medications).
 - Patients who have initiated weight loss drugs (including OTC and herbal medications) within 3 months before the screening period should be excluded from the trial.
- Use of systemic glucocorticoids (excluding topical application or inhaled forms) for > 14 consecutive days.
- Other medications are allowed as needed; however, doses of chronically administered medicines should be kept fixed during the trial if at all possible.

CCI

6 Trial Assessments and Procedures

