8.1.2 Estimands

Attributes for the primary and supplementary estimands with the strategies used for handling ICEs are presented in [Table 8-2](#).

Table 8-2 Primary and Supplementary Estimands

Estimand 1a (Primary)	
Estimand Description	Difference in the mean change from baseline to Week 24 in HbA1c level (Gla-300 vs IDeg-100) in insulin-naïve patients with T2DM and renal impairment who have glycemic levels above target with OADs with or without GLP-1 RA (oral or injectable), regardless of discontinuation of study drug treatment due to any reasons and use of rescue therapies
Target Population	Insulin-naïve patients with T2DM and renal impairment who have glycemic levels above target with OADs with or without GLP-1 RA (oral or injectable) as defined by the inclusion/exclusion criteria (Section 4)
Treatment Conditions	Once daily, SC self-injection of Gla-300 versus IDeg-100 with the planned dose modifications outlined in Section 5.5.1 
• Gla-300: Insulin glargine 300 U/mL• IDeg-100: Insulin degludec 100 U/mL
Endpoint	Change in HbA1c level from baseline to Week 24
Population Level Summary	Difference in the mean change in HbA1c level from baseline to Week 24 between Gla-300 and IDeg-100

Estimand 1a (Primary)	
ICEs and Strategies	Treatment policy strategy for handling the ICEs in Table 8-1
Rationale	Using the treatment policy strategy for handling ICEs is considered appropriate for showing superiority (ICH E9 R1), which allows switching the objective of a trial from non-inferiority to superiority (CPMP guideline)
Estimand 1b (Supplementary)	
Estimand Description	Difference in the mean change from baseline to Week 24 in HbA1c level (Gla-300 vs IDeg-100) in insulin-naïve patients with T2DM and renal impairment who have glycemic levels above target with OADs with or without GLP-1 RA (oral or injectable), assuming no discontinuation of study drug treatment due to any reasons and use of rescue therapies
Target Population	Insulin-naïve patients with T2DM and renal impairment who have glycemic levels above target with OADs with or without GLP-1 RA (oral or injectable) as defined by the inclusion/exclusion criteria (Section 4)
Treatment Conditions	Once daily, SC self-injection of Gla-300 versus IDeg-100 with the planned dose modifications outlined in Section 5.5.1 
 • Gla-300 arm: Insulin glargine 300 U/mL • IDeg-100 arm: Insulin degludec 100 U/mL

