5.3.4.2 Antidiabetic medications

Prior, concomitant, and post-treatment antidiabetic medications will be summarized by pharmacological class (ATC3), chemical class (ATC4) and standardized medication name for the ITT population and will be presented by treatment arm and overall.

The table for antidiabetic prior medications will be sorted by decreasing frequency of pharmacological class followed by chemical class and standardized medication name based on the overall incidence across treatment arm. In case of equal frequency, alphabetical order will be used.

The tables for antidiabetic concomitant and post treatment medications will be sorted by decreasing frequency of pharmacological class followed by chemical class and standardized medication name based on the incidence in the Gla-300 treatment arm. In case of equal frequency, alphabetical order will be used.

In addition, the following specific medications will be summarized:

- Antidiabetic concomitant rescue medications will be presented by pharmacological class (ATC3), chemical class (ATC4) and standardized medication name. [Table 9](#) below defines antidiabetic medications by pharmacological class (ATC3).

- Prohibited concomitant medications will be presented by prohibited medication category (as defined by deviation) and standardized medication name (see [Table 8](#) below).

Table 8 - Prohibited Medications

Prohibited Medication Category	Pharmacological Class (ATC3)	Standardized Medication Name (ATC4) ^a
Insulins and analogues	A10AB, A10AC, A10AD, A10AE, A10AF	
Other blood glucose lowering drugs, excluding insulins	A10BX	Tirzepatide (ATC5: A10BX16)
Peripherally acting antiobesity products	A08AB	
Thyroid hormones	H03AA	
Corticosteroids (excluding inhaled and topical)	H02A, H02B	
Salicylic acid and derivatives	N02BA	
Ascorbic acid (Vitamin C), including combinations	A11GA, A11GB, G01AD, S01XA	Ascorbic acid (G01AD03), Ascorbic acid (S01XA15)

^a Standardized medication names are provided where the prohibited medication is limited to certain medications within the provided ATC3 class.

A list of ATC3 codes to be used in identifying antidiabetic medications is shown in [Table 9](#) below. Prior, concomitant and post-treatment antidiabetic non-insulin and rescue therapies will also be summarized per standardized drug grouping name and standardized medication name.

Table 9 - Antidiabetic Medications

Standardized Drug Grouping Name	Group ID	Pharmacological Class (ATC3)

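### The Section 4.4.3 withdrawal rule for drugs that affect glucose metabolism has no duration and does not say what is stopped, out of step with the 14-day limit in Section 5.11 and Exclusion 11

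*Protocol*

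**What the plan says.** **The withdrawal rule.** Protocol Section 4.4.3 introduces a list of circumstances with "A patient may withdraw from the trial or study drug treatment for circumstances that include". One item reads "The patient will be withdrawn if they are starting any drugs that interfere with glucose metabolism (eg, systemic glucocorticoid therapy"). It gives no minimum duration and does not say whether study drug or trial participation ends.

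**The medication rule.** Protocol Section 5.11 lists what is not permitted during screening and treatment. The glucocorticoid entry is "Use of systemic glucocorticoids (excluding topical application or inhaled forms) for > 14 consecutive days". The list closes with "Other medications are allowed as needed", qualified by a request to keep long-term doses fixed where possible.

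**The entry rule.** Exclusion 11 (Section 4.2) covers drugs known to affect weight or glucose metabolism, with corticosteroids among its examples. It applies the same threshold of more than 14 consecutive days and sets aside topical and inhaled forms.

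**The stance on stopping treatment.** Section 4.4.1 says "permanent study drug discontinuation should be the last resort". For those who do stop, Section 4.4.1.1 says "Patients will be followed up according to the trial procedures specified in this protocol up to the scheduled date of trial completion", or until any adverse event has recovered or stabilized if that is later.

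**The estimand.** For Estimand 1a, Table 8-2 specifies "Treatment policy strategy for handling the ICEs in" Table 8-1, namely study drug discontinuation for any reason and rescue therapy.

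**The concern.** A patient given a short systemic glucocorticoid course, for example for an acute illness, is treated differently depending on which section the site consults. Section 5.11 does not prohibit the course. Section 4.4.3, taken at its word, removes the patient when the course starts.

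The second gap is what removal means. A treatment-policy estimand needs the Week 24 HbA1c whether or not study drug continues. A rule that can be read as trial exit works against that, because it may discard a value that could have been observed. Sites may also resolve the ambiguity differently.

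**Working it through.** No arithmetic decides this point, so the check compares the provisions and follows one case through them.

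**1. Duration.**

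| Provision | Drugs | Duration | Applies to |
|---|---|---|---|
| 4.2, Exclusion 11 | Drugs affecting weight or glucose metabolism, including non-topical, non-inhaled corticosteroids | >14 consecutive days | Entry |
| 5.11 | Systemic glucocorticoids, topical and inhaled forms aside | >14 consecutive days | Screening and treatment |
| 4.4.3 bullet | Any drug interfering with glucose metabolism, systemic glucocorticoids as the example | None; acts at the start | Withdrawal |

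A course of 14 days or less falls outside the first two rows and inside the third. If every start led to withdrawal, the 14-day limit in 5.11 would have little purpose during treatment.

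**2. What is stopped.** Take a patient who starts a 7-day oral course, a length chosen only for illustration.

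- *Study drug only.* Follow-up continues to scheduled completion (4.4.1.1). The event is the first intercurrent event in Table 8-1, and Week 24 HbA1c can be collected and used for Estimand 1a. Even so, a permanent stop for a short course fits poorly with Section 4.4.1.
- *Trial exit.* Section 4.4.3 calls for an early discontinuation visit, and Section 6.1.1 for an HbA1c at withdrawal if possible. SAP Section 4.3.1 treats HbA1c results outside the baseline, Week 12 and Week 24 windows as missing. SAP Table 10 sets those windows:
  - Sample before Day 72: no usable post-baseline HbA1c.
  - Sample on Days 72 to 127: counts as Week 12, and Week 24 is missing.
  - Sample on Day 128 or later: counts as Week 24. This can be up to 169 − 128 = 41 days before the target day.

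Under the second reading, an exit sample on any of the first 127 study days leaves Week 24 missing.

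**3. Consequence for imputation.** Protocol Section 8.7.3.1 and SAP Section 4.3.2 impute missing values for discontinuers from same-arm discontinuers whose endpoint was observed. The study-drug reading can add such donors. The exit reading before Day 128 adds missing values and no donors. SAP Section 4.3.2 already foresees too few donors and then samples around the baseline value.

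**4. Breadth.** Rescue therapy means a new antidiabetic drug or a higher dose of an existing one, with prandial insulin a possible preferred option (5.2.2). A new drug of that kind acts on glucose metabolism, so the bullet's words cover it. Section 5.2.2 says the opposite: rescued patients stay in the trial and on study drug, and Table 8-1 treats rescue as an intercurrent event.

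**The case against.** The strongest reply is that the protocol's intention is clear and only its wording slips.

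- *Exclusion 11 shows the intended meaning.* It uses the 14-day threshold for nearly the same drug class. This stands. A reader might infer that nothing in the documents indicates a duration, and that would be wrong. Exclusion 11 governs entry, however, so it shows what the bullet should say without changing what it does say.
- *The list is permissive.* Its lead-in says *may*. This stands in part, and calling the rule plainly mandatory would go too far. But this item says *will*, while the neighbouring items on noncompliance and on glucose above 300 mg/dL say *may*, so a site could reasonably read it as compulsory.
- *Not prohibited is not the same as expressly allowed.* Section 5.11 names short insulin use as allowed and gives no such permission for short glucocorticoid courses. It also conditions added treatments on being unlikely to interfere with study drug. This stands: 5.11 does not prohibit short courses, and no more can be claimed.
- *Every item in the list leaves the route open, each route is described, and temporary interruption exists.* True. Section 4.4.1.2 allows interruption for other medical issues, but the bullet speaks of withdrawal and does not point there.

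A reader might also take SAP Table 8, whose row "Corticosteroids (excluding inhaled and topical") has no time limit, as a third conflicting rule. The table maps medication categories to ATC codes for tabulation and gives no durations anywhere. Insulins appear there without the short-use or rescue allowances, so its silence on duration proves nothing.

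**Conclusion.** The point holds as a minor inconsistency in the plan as written. The bullet has no duration where two related provisions use 14 days, it leaves open what is stopped, and its literal scope includes rescue therapy. If a site reads it as trial exit, a Week 24 HbA1c that Estimand 1a needs is avoidably lost unless an exit sample falls on or after Day 128. If only study drug is stopped, that value need not be lost.

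A reader might infer a loss of power or a bias between arms. The documents do not support either. They give no rate of glucocorticoid use and no reason to expect it to differ by arm, and such withdrawals may already sit within the planned 10% dropout. Neither size nor direction can be derived.

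Nor does the point affect reported results. SAP Section 1.1 records early termination on 27 June 2023 for slow recruitment, and SAP Section 5.2 limits primary and secondary efficacy to descriptive summaries. The conclusion rests on the literal text and does not depend on how sites actually applied it.

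**What to change.** Reword the Section 4.4.3 bullet in three respects:

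1. Limit it to systemic glucocorticoids (topical and inhaled forms excluded) and other non-antidiabetic drugs affecting glucose metabolism, when used for more than 14 consecutive days. This matches Section 5.11 and Exclusion 11.
2. State that rescue therapy permitted under Section 5.2.2 is not a trigger.
3. State that at most study drug is stopped, and that scheduled visits with Week 12 and Week 24 HbA1c continue. This goes beyond aligning durations; the reason is the treatment-policy estimand.

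The cost is the wording of one protocol bullet. The visits and HbA1c assays are already in the schedule of events (Section 13.2), and Section 5.11 already requires administration dates for concomitant medication. As the trial has ended, the practical value lies in any later protocol that reuses this text.

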4.4.4 Replacements

Patients who discontinue the trial will not be replaced.

5 Trial Treatments

5.1 Study Drug

The study drugs are Gla-300 or IDeg-100 and will be supplied as prefilled, disposable pens (Gla-300 as a SoloStar® pen and IDeg-100 as a FlexTouch® pen). The details are provided in [Table 5-1](#).

An instruction leaflet will be provided to patients that explains how to use the disposable pen and needles. All patients will be trained by site staff at Visit 2 (baseline/randomization) on how to use the pen correctly, how to store it, and how to change the needle and to ensure patients are able to self-inject (eg, set correct dose, change the needle, identify the correct injection area, complete the injection, know the appropriate storage conditions, conduct simple troubleshooting). The patient's family member or usual caregiver, if applicable, is highly encouraged to attend the training with the patient, as they play a key role and are able to support the patient with trial-related procedures during the trial. Training will be repeated during the treatment period as often as deemed necessary by site staff. These training/re-training details should be documented in the patient's source documents.

For the duration of treatment, patients will be required to use the same type of disposable pens and needles. The pen and leaflet that patients will need to use during the treatment period will be dispensed at the time points specified in the SoE ([Section 13.2](#)). Each patient will be supplied with the appropriate number of pens according to the dispensing scheme indicated in the SoE ([Section 13.2](#)).

Injection pens should never be shared with others, even if the needle is changed. Patients must always use a new needle for each injection to help ensure sterility and prevent blocked needles.

Table 5-1 Overview of Study Drug To Be Administered

Formulation	Gla-300	IDeg-100
Dosage formulation	Gla-300 will be supplied as a sterile, nonpyrogenic, clear, colorless solution in a SoloStar prefilled (disposable) pen for SC injection.	IDeg-100 will be supplied as a sterile, nonpyrogenic, clear, colorless solution in a FlexTouch prefilled (disposable) pen for SC injection.
Unit dose strength(s)/Dosage level(s)	Each Gla-300 SoloStar pen contains 450 U of insulin glargine (1.5 mL of 300 U/mL insulin glargine solution).	Each IDeg-100 FlexTouch pen contains 300 U of insulin degludec (3 mL of 100 U/mL insulin degludec solution).
Route of administration	The study drug will be administered via SC self-injection into the abdominal area, thigh, or upper arm using the SoloStar pen or FlexTouch pen. Injection sites should be rotated within the same region from 1 injection to the next to reduce the risk of lipodystrophy. (Note: The injection sites for study drug and NIMP, if taken, should be different so that any injection site reactions can be attributed specifically to the study drug or NIMP [eg, GLP-1 RA].)	

Abbreviations: Gla-300, insulin glargine 300 U/mL; GLP-1 RA, glucagon-like peptide-1 receptor agonist; IDeg-100, insulin degludec 100 U/mL; NIMP, non-investigational medicinal product; SC, subcutaneous.

